Ongoing subjects will continue to administer the remainder of dispensed vials as per the dose regimen prior to Amendment 4 until their first visit with Study Drug Dispensing after Amendment 4 when they will transition to the fixed dose regimen.

[figure not shown]
The duration of the study could be up to 298 weeks, which includes a 288-week open-label maintenance period and a 70-day follow-up. There is a \pm 3 day window for all study visits. An effort will be made to bring subjects back to their original scheduled visit (calculated from Baseline) if they are out of the visit window.

Efficacy and safety measurements will be performed throughout the study (see Table of Activities, Section 5.3.1). Clinical evaluation will be performed at Baseline, Weeks 4, 8, 12, 24, 36, 48, 60, 72, 84, 96, 108, 120, 144, 168, 192, 216, 240, 264 and 288/Premature Discontinuation and unscheduled Visits. Subjects may undergo an optional endoscopy during Weeks 48, 96, 192, and 288/Premature Discontinuation Visit to assess disease activity and for surveillance per the investigator's discretion.

Treatment of Subjects with a Disease Flare

Criteria for Disease Flare are as follows:

- Subjects with a Baseline Study M10-870 PMS of 0 to 2 who present with a PMS at least 3 points greater than their Baseline Study M10-870 score.
- Subjects with a Baseline Study M10-870 PMS of 3 to 4 who present with a PMS at least 2 points greater than their Baseline Study M10-870 score.
- Subjects with a Baseline Study M10-870 PMS of 5 to 6 who present with a PMS at least 1 point greater than their Baseline Study M10-870 score.
- Subjects who present with a PMS of at least 2 points greater than their PMS at the previous visit and who are not in remission per PMS.

Prior to Amendment 4:

- Subjects with a disease flare who were on 0.6 mg/kg (maximum dose of 40 mg, weight based) eow of adalimumab could receive 0.6 mg/kg (maximum of 40 mg, weight based) ew of adalimumab.
- Subjects with a disease flare who were on 0.6 mg/kg ew of adalimumab could receive 40 mg ew (maximum dose of 40 mg).

Subjects with persistently uncontrolled disease while on adalimumab 40 mg ew (max dose) were to be discontinued from the study.

After Amendment 4:

[figure not shown]
- Subjects who are on 20 mg eow of adalimumab may receive 40 mg eow of adalimumab.
- Subjects who are on 40 mg eow of adalimumab may receive 80 mg eow of adalimumab.

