- a. The Baseline visit date will serve as the reference for all subsequent visits. $A \pm 3$ -day window is permitted around scheduled study visits.
- b. Procedures performed as needed.
- c. Site personnel will contact all subjects approximately 70 days following study drug discontinuation to determine the occurrence of AEs or SAEs.
- d. At the Baseline visit, the following procedures for Study M10-870 will be completed as part of Week 52 of the Study M11-290 protocol: tobacco & alcohol use; concomitant medication changes, physical exam, vital signs, Chemistry/hematology, hs-CRP; PUCAI; urinalysis, pregnancy test; TB testing, Partial Mayo Score; Mayo Score, IMPACT III Questionnaire, WPAI UC-Caregiver, Tanner Stage, Anthropometric Evaluations, X-ray for Bone age; endoscopy, adverse events and subject diary dispensing/reviewing. Medical History will be updated from the medical history recorded during the subject's previous study.
- e. Vital sign determinations of weight, sitting blood pressure, pulse rate, respiratory rate, body temperature will be obtained at each visit.
- f. The endoscopy is optional at Weeks 48, 96, 192 and 288/Premature Discontinuation. In this case, endoscopies may be either flexible sigmoidoscopy or colonoscopy. Biopsies to rule out malignancy, dysplasia, and infection may be taken at the investigator's discretion. Mayo score is dependent on availability of endoscopy.
- g. Physical examinations performed at Weeks 48, 96, 144, 192, 240, and 288/Premature Discontinuation Visits are full physical examinations and those performed at all other visits are symptom based.
- h. For subjects with a negative TB test, a TB test will be required at Weeks 48, 96, 144, 192, 240 and 288. If the annual TB screen is positive, a CXR may be required for evaluation of active TB. Annual TB screening will not be required for subjects who have been treated for latent or active TB or have had a positive TB test at any time (prior to the study, or testing performed at any time point during Study M11-290). For such subjects, annual evaluation by a physician for clinical signs/symptoms of active TB (including a directed TB history and physical exam including lungs, lymph nodes and skin) or newly identified TB risk factors will be required at Weeks 48, 96, 144, 192, 240 and 288.
- i. Blood draws should be performed after completion of all clinical assessments and questionnaires.

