The PUCAI score will be assessed using subject-reported symptoms and activity level. The answers should reflect symptoms and activity level during the previous 24 hours. The PUCAI scores of the last 2 days prior to each study visit will be averaged and used for the PUCAI scores for each study visit. The total PUCAI score will be rounded up to the next 5-point interval as applicable. In order to account for unavailable or excluded diary entries as per the provisions given below diary entries for the PUCAI score of the most recent 2 days within 10 days prior to each study visit will be used.

Diary entries of the following days should not be included in the 2 days prior to the visit that are evaluated for the PUCAI score: (1) the day the subject received medication for bowel preparation prior to endoscopy, (2) the day the subject underwent an endoscopy, and (3) 2 days following the endoscopy. Earlier diary entries will be used accordingly in order to provide the most recent data for 2 days prior to the respective study visit.

The subscore for the number of stools per 24 hours during days which a subject received anti-diarrheal medication will be scored as 15.

Mayo Score

All subjects will be provided with a Subject Diary at the Baseline Visit where they will record ulcerative colitis related symptoms. The Partial Mayo Score will be calculated from the subject diary at each visit beginning at Baseline. The average entry from the 5 days prior to each study visit will be used for each subject-reported subscore. In addition to the physical examination, the investigator should use the subject-reported

subscores of abdominal discomfort and functional assessment to determine the physician's global assessment subscore.

Normal number of bowel movement is the number of stools per day (24 hours) that is typical for the subject when having active UC but not experiencing a flare. Each subject serves as his or her own control to establish the degree of abnormality of the stool frequency.

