For composite scores which consist of several component subscores, components will be imputed first and the composite score will be calculated based on imputed component subscores. Only if composite score still can't be calculated after imputing component subscores, then the previous composite score will be carried forward.

[figure not shown]

Missing Items on Questionnaire Scales:

Mayo scores (and alternative composite scores) can only be calculated if all subscores included are collected. If one or more subscores are missing, the score will be considered missing. No imputations will be made. The symptoms of stool frequency and rectal bleeding are scored as a 5 day average of daily values from up to 14 days preceding the visit, rounded to one decimal place. The most recent consecutive days will be used. If consecutive days are not available, then non-consecutive days can be used. Diary entries for stool frequency and rectal bleeding should not be included in the 5 days prior to the visit that are evaluated for these subscores for the following days: (1) the day the subject received medication for bowel preparation prior to endoscopy, (2) the day the subject underwent an endoscopy, and (3) 2 days following the endoscopy. Earlier diary entries will be used accordingly in order to provide the most recent data for 5 days prior to the respective study visit. If less than 3 days of diary data are available, stool frequency and rectal bleeding subscores will be considered missing.

[figure not shown]
When calculating **PUCAI**, if more than 3 subscores are missing then PUCAI will be considered missing. Otherwise, for missing subscores, the last available post-baseline value for the respective subscore will be carried forward to compute the total PUCAI score. The subscores of abdominal pain, rectal bleeding, stool consistency, number of stools per 24 hours, nocturnal stools and activity level are scored as a 2 day average, rounded to one decimal place. The most recent consecutive days will be used. If consecutive days are not available, then non-consecutive days can be used.

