Partial Mayo Score	Composite score of UC disease activity based on the subscores of stool frequency, rectal bleeding, and physician's global assessment and DOES NOT include the endoscopic subscore. This score ranges from 0 – 9 points with higher scores representing more severe disease.	
9 point Mayo Score (without PGA)	Composite score of UC disease activity based on the subscores of stool frequency $(0-3)$, rectal bleeding $(0-3)$, and endoscopic subscore $(0-3)$. This score ranges from $0-9$ points with higher scores representing more severe disease.	
6 point Mayo Score (without PGA and endoscopy subscore)	Composite score of UC disease activity based on the subscores of stool frequency $(0-3)$ and rectal bleeding $(0-3)$. This score ranges from $0-6$ points with higher scores representing more severe disease.	

[figure not shown]

Table 2. Definition of Endpoints Based on Mayo Score and Component Scores

Term	Definition
Clinical remission per Partial Mayo Score	PMS ≤ 2 and no individual subscore ≥ 1
Clinical response per Partial Mayo Score	Decrease in PMS \geq 2 points and \geq 30% from Study M11-290-Baseline
Clinical remission per Mayo Score	Mayo score ≤ 2 and no individual subscore > 1
Clinical response per Mayo Score	Decrease in Mayo Score \geq 3 points and \geq 30% from Study M11-290-Baseline
Mucosal healing	Endoscopy subscore of 0 or 1
Clinical remission per 9 point Mayo Score (without PGA)	Defined as the 9 point Mayo Score (without PGA) \leq 2 and no individual subscore $>$ 1
Clinical remission per 6 point Mayo Score (without PGA and endoscopy subscore)	Defined as the 6 point Mayo Score (without PGA and endoscopy subscore) ≤ 1

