10.2 Efficacy Analysis

The efficacy endpoints are:

- The proportion of subjects who achieve clinical remission as measured by PMS (defined as a PMS ≤ 2 and no individual subscore ≥ 1) over time;
- The proportion of subjects who achieve clinical response as measured by PMS (defined as a decrease in PMS ≥ 2 points and ≥ 30% from Study M11-290-Baseline) over time;
- The proportion of subjects who achieve PUCAI remission (defined as < 10) over time;
- The proportion of subjects who achieve PUCAI response (defined as a decrease in PUCAI ≥ 20 points from Study M11-290-Baseline).
- Change from Baseline in total IMPACT III Quality of Life score and subscores over time for subjects at least 9 years old at Baseline;
- Change from Baseline in WPAI scores over time;
- Change from Baseline in "z" scores for height over time;
- Change from Baseline in BMI over time;
- Change from Baseline in "z" scores for weight-for-age over time;
- Change from Baseline in albumin and total protein over time;
- Change from Baseline in hemoglobin, hematocrit, red blood cell count over time;
- Change from Baseline in hs-CRP levels over time;
- Proportion of subjects at appropriate Tanner stage (see Section 6.0) over time;
- Proportion of subjects in Mayo score clinical response over time (for subjects with available Mayo score);
- Proportion of subjects in Mayo score clinical remission over time (for subjects with available Mayo score);
- Proportion of subjects who achieve mucosal healing over time as measured by Mayo endoscopy subscore (defined as ≤ 1, for subjects with available Mayo score)
- Proportion of subjects in 9 point Mayo score (without PGA) clinical remission over time (for subjects with available Mayo score);

• Proportion of subjects in 6 point Mayo score (without PGA and endoscopy subscore) clinical remission over time (for subjects with available Mayo score).

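### SAP 10.2 ties 6 point Mayo remission, a diary-only endpoint, to having a Mayo score; read literally and visit by visit, at most 4 of 19 post-baseline visits contribute

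*SAP*

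**What the plan says.** SAP section 10.2 ends its efficacy list with the proportion of subjects in "6 point Mayo score (without PGA and endoscopy subscore) clinical remission over time (for subjects with available Mayo score").

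SAP section 6.0 (Score Definitions, Table 1) builds the 6 point score from stool frequency and rectal bleeding alone. Table 2 defines remission on it as a score of 1 or less. The same Table 1 defines the Mayo Score as four subscores, one of them endoscopic.

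On the source of the two components, SAP section 6.0 states: "The symptoms of stool frequency and rectal bleeding are scored as a 5 day average of daily values". Protocol section 5.3.1.1 states: "The Partial Mayo Score will be calculated from the subject diary at each visit beginning at Baseline". The PMS contains both subscores.

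On the full score, footnote f to protocol Table 1 states: "Mayo score is dependent on availability of endoscopy". Protocol section 5.3.1.1 leaves endoscopy to the investigator's discretion at Weeks 48, 96, 192 and 288/Premature Discontinuation. SAP section 6.0 (Definition of Analysis Windows) shows each measure only at the visits where it was planned, and uses the Mayo score as its example.

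**The concern.** The restriction makes sense for Mayo response, Mayo remission, mucosal healing and the 9 point score, all of which need an endoscopy. The 6 point score does not. Applying the same condition to it makes a diary endpoint depend on a procedure that is optional and that the investigator decides on.

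Two things are at stake. One is precision: visits and subjects with usable diary data would drop out of the denominator. The other is selection: if the decision to scope is related to how the subject is doing, the remission proportion describes a selected group. The 6 point score is also the only Mayo-type endpoint in the list with neither the endoscopy subscore nor the physician's global assessment, so the restriction works against the reason for having it.

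**Working it through.** The plan gives no figure for this point, so there is none to reproduce. The check is a count of visits, followed by illustrations under stated assumptions.

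**1. Does anything else in the plan require endoscopy for the 6 point score?** No.
- SAP section 6.0 (Missing Items on Questionnaire Scales) lets an alternative composite be calculated when its own included subscores are present.
- SAP section 5.1 uses the Full Analysis Set for all analyses.
- Protocol section 5.3.2 applies the availability condition only to Mayo remission and response and to mucosal healing. It does not mention a 6 point score.

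**2. Visits.** Protocol section 5.1 schedules post-baseline evaluations at "Weeks 4, 8, 12, 24, 36, 48, 60, 72, 84, 96, 108, 120, 144, 168, 192, 216, 240, 264 and 288/Premature Discontinuation", which is 19 visits. Table 1 of the protocol has PMS at each of them. A full Mayo score is planned post-baseline at 4 (Weeks 48, 96, 192 and 288/Premature Discontinuation).
- Share of visits that can contribute: 4/19 = 21.1%.
- Share that cannot: 15/19 = 78.9%.

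**3. Subject-visits.** SAP section 4.3 expects 55 subjects outside Japan, the population of this SAP. Assume no dropout and complete diaries.
- Without the restriction: 55 × 19 = 1045.
- With it: 55 × 4 × uptake. The documents do not give endoscopy uptake, so a range is shown.

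| Assumed uptake | Subject-visits kept | Share of 1045 |
|---|---|---|
| 100% | 220 | 21.1% |
| 50% | 110 | 10.5% |
| 25% | 55 | 5.3% |
| 10% | 22 | 2.1% |

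**4. Precision at one visit.** Assume about 60% in remission and use exact (Clopper-Pearson) 95% intervals.
- All 55 subjects: 33/55, interval 45.9% to 73.0%.
- 25% uptake (55 × 0.25 = 13.75, taken as 14): 8/14, interval 28.9% to 82.3%. The width goes from 27.1 to 53.5 percentage points.

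**5. Selection.** Let p be true remission, a the endoscopy rate in remitters and b the rate in non-remitters. The observed proportion is p·a / [p·a + (1 − p)·b]. Take p = 60% as an assumption.
- a = 20%, b = 40%: 0.12 / (0.12 + 0.16) = 42.9%.
- a = 40%, b = 20%: 0.24 / (0.24 + 0.08) = 75.0%.
- a = b: 60.0%, no bias.

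The rates a and b are illustrative. The documents give neither, so neither the size nor the direction of any bias can be derived from them.

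**The case against.** A reader might infer that the plan certainly discards 79% of this endpoint's data. The documents do not go that far.

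- **The condition names subjects, not visits.** Protocol section 5.3.1.1 takes a Baseline Mayo score from Week 52 of Study M11-290, and the SAP lists Week 0 among the Mayo collection points. If that score qualifies a subject, few may be excluded.
- **The wording may be carried over.** The same parenthesis closes all five Mayo-family endpoints. For this one it may mean only that the 6 point score itself is available, which would fit the SAP's scoring rule.
- **LOCF softens the loss.** SAP section 10.1 plans OC and LOCF, and section 6.0 imputes component subscores before the composite. A subject scoped at Week 48 but not at Week 96 could therefore have a Mayo score at Week 96 under LOCF. LOCF does not bring back visits at which no Mayo score was planned.

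A reader might also infer that the estimate is biased, or that the report would lack a symptom-only remission measure. Neither is supported. Step 5 shows that selection is possible, not that it occurs. PMS remission is reported over time without the restriction, and so is PUCAI remission, which uses subject-reported items with neither the physician's assessment nor endoscopy.

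Finally, showing the full, 9 point and 6 point scores in the same subjects is a coherent like-for-like comparison. The SAP does not state that purpose, and an additional line serves it equally well.

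What stands is that the SAP's definition of Mayo Score and its display rule make the literal visit-level reading a natural one. The competing readings lead to materially different denominators, and the SAP does not choose between them.

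**Conclusion.** The point holds as a fault in how the endpoint is specified. Under the literal, visit-level, observed-case reading, at most 4 of 19 post-baseline visits (21%) contribute, and at those only subjects who had an endoscopy at the investigator's discretion. The 21% rests on that reading and on the scheduled visits. Any further loss depends on endoscopy uptake, which is not given. Under a subject-level reading that counts Week 0, or under LOCF, the loss is smaller.

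The consequence is lower precision and possible selection of unknown direction. The impact is modest: this is the last of 18 descriptive endpoints, SAP section 10.1 rules out confirmatory testing, and PMS and PUCAI remission are reported without the condition. No conclusion of the study turns on it. The change is still worth making, because it is a free improvement.

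**What to change.** In SAP section 10.2, for the 6 point endpoint only, replace the closing parenthesis with a condition that both diary subscores are available. Report the endpoint in the Full Analysis Set at every visit where PMS is reported, with OC and the planned imputation, and show n at each visit.

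If a comparison with full and 9 point Mayo remission in the same subjects is wanted, keep the endoscopy-subset version as an additional, labelled line. State there whether availability is judged per visit or per subject, and whether Week 0 counts.

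The diary data are already collected, so the cost is one changed phrase and some extra table rows.

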10.3 Handling of Multiplicity

Not applicable since no confirmatory testing is performed.

10.4 Efficacy Sensitivity Analyses

Sensitivity analyses may be performed as deemed appropriate.

10.5 Efficacy Subgroup Analysis

[figure not shown]
The subgroups listed below will be used for proportions of subjects with PMS remission and Mayo score clinical remission over time.

- Sex (male, female)
- Age ($< 13 \text{ years}, \ge 13 \text{ years}$)
- Geographic region (North America, Western Europe, Eastern Europe)
- Prior (prior to Study M11-290) anti-TNF use (yes, no)
- Baseline systemic corticosteroid use (yes, no)
- Baseline IMM use (yes, no)
- Weight ($< 40 \text{ kg}, \ge 40 \text{ kg}$)
- Pancolitis (yes, no)
- Disease duration (\leq Baseline-median, \rightarrow Baseline-median)

11.0 Safety Analysis

11.1 General Considerations

Incidence of adverse events (AEs), changes in vital signs, physical examination results, and clinical laboratory data are the safety parameters in this study.

[figure not shown]

11.2 Analysis of Adverse Events

Treatment emergent AEs, serious adverse events (SAEs), and AEs of special interest will be summarized.

AEs of special interest include:

- Infections
- Serious infections
- Opportunistic infections excluding oral candidiasis and tuberculosis (TB)
- TB (active/latent)
- Oral candidiasis
- Legionella infections
- Parasitic infections
- Diverticulitis
- Malignancies
- Lymphoma
- Hepatosplenic T-cell lymphoma (HSTCL)
- Leukemia
- Non-melanoma skin cancer (NMSC)
- Melanoma
- Malignancy other than lymphoma, HSTCL, leukemia, NMSC or melanoma
- Lupus-like reactions and systemic lupus erythematosus
- Allergic reactions including angioedema/anaphylaxis
- Stevens-Johnson syndrome
- Sarcoidosis
- Vasculitis (cutaneous/non-cutaneous)
- Demyelinating disorder
- Interstitial lung disease
- Congestive heart failure (CHF)
- Myocardial infarction (MI)

[figure not shown]

- Cerebrovascular accident (CVA)
- Intestinal perforation
- Pancreatitis
- Hematologic disorders including pancytopenia
- Liver failure and other liver events
- Reactivation of Hepatitis B
- Autoimmune Hepatitis
- Injection site reaction
- Erythema multiforme
- Worsening or new onset of psoriasis
- Pulmonary embolism
- Progressive multifocal leukoencephalopathy (PML)
- Reversible posterior leukoencephalopathy syndrome (RPLS)
- Amyotrophic lateral sclerosis
- Humira administration related medication error

Treatment-emergent AEs are defined as events with an onset date after the first dose of the study drug in Study M10-870 (i.e., on/after Rx Day 1) and with an onset date no more than 70 days after the last dose of the study drug in Study M10-870.

AEs with missing or unknown severity will be categorized as severe. AEs with missing or unknown relationship to study drug will be categorized as 'Reasonable Possibility' of being related to study drug. AEs that are reported more than 70 days after last dose of study drug will be excluded from the AE summaries; however, all reported AEs will be included in the AE data listings.

Overview tables of number and percentage of subjects with treatment-emergent AEs and events per 100 patient-years of ADA exposure in Study M10-870 (as defined in Section 9.0) will be provided.

AE data will be summarized and presented using primary MedDRA system organ classes (SOCs) and preferred terms (PTs) according to the version of the MedDRA coding dictionary used to code the AE data. The system organ classes will be presented in alphabetical order and the preferred terms will be presented in alphabetical order within each system organ class.

In addition, a summary of AEs by maximum severity and relationship to study drug will be presented.

A subject who reports more than one AE in different system organ classes will be counted only once in the overall total. A subject who reports two or more different preferred terms which are in the same SOC will be counted only once in the SOC total. A subject who reports more than one AE with the same preferred term will be counted only once for that preferred term using the most extreme incident (i.e., most "severe" for the severity tables and as having a 'Reasonable Possibility' of being related to study drug for the relationship tables).

[figure not shown]
Summaries by subject number and listings will also be provided as appropriate.

An overview of AE categories by type of output is provided below:

Adverse Event Overview

The number and percentage of subjects experiencing treatment-emergent AEs, as well as events per 100 PYs, will be summarized for the following AE categories:

[figure not shown]
- o Any AE
- SAEs
- Severe AEs
- AEs leading to discontinuation of study drug
- AEs rated as possibly related to study drug by the investigator (reasonable possibility)

- SAEs rated as possibly related to study drug by the investigator (reasonable possibility)
- AEs leading to Death
- AEs of special interest
- Adverse Events by System Organ Class and Preferred Term

The number and percentage of subjects experiencing treatment-emergent AEs, as well as events per 100 PYs, will be summarized by SOC and PT for the following AE categories.

- o Any AE
- SAEs
- AEs leading to discontinuation of study drug
- Subject Numbers Associated with treatment-emergent Adverse Events by System Organ Class and Preferred Term
 - o Any AE
- Adverse Event listing
 - o Any AE
 - SAEs
 - Severe AEs
 - AEs leading to discontinuation of study drug
 - AEs rated as possibly related to study drug by the investigator (reasonable possibility)
 - SAEs rated as possibly related to study drug by the investigator (reasonable possibility)
 - AEs leading to Death
 - AEs of special interest

[figure not shown]

